#### *Secondary outcomes:*

In addition, the 50% response rate will be calculated between weeks 20 and 24, compared to the baseline situation, as well as the 75% and 30% response rates, both between weeks 8 and 12 and 20 and 24.

The proportion of patients experiencing adverse effects and discontinuing treatment because of them will be reported.

As study subgroups, the response and tolerability will be specifically evaluated in women and elderly patients, using the previously defined variables, in women, patients over 65 years of age and over 80 years of age.

All these variables will be presented with their corresponding 95% confidence intervals.

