**Response predictors:**

To assess which variables are associated with a greater probability of response, a logistic regression analysis will be performed in which the dependent variable will be the presence of a 50% response between weeks 8 and 12 of treatment.

First, a univariate logistic regression analysis will be carried out in which all study variables, demographic, clinical, and treatment-related will be evaluated. Those variables with a *P* value lower or equal to 0.2 will be included in a multivariate model.

A statistical significance level of 0.05 will be considered. For the adjustment for multiple comparisons, the adjustment according to False Discovery Rate will be used using the Benjamini-Hochberg method.

Statistical analysis will be performed using SPSS (IBM).

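### Do the subgroup rates for women, over-65s and over-80s need a comparison group and a between-group estimate?

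*SAP*

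**What the plan says.** The SAP's Secondary outcomes section sets the subgroup aim: "the response and tolerability will be specifically evaluated in women and elderly patients, using the previously defined variables". The groups are then listed: "in women, patients over 65 years of age and over 80 years of age".

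The variables to be used in them are the response rates (50% in both windows, "as well as the 75% and 30% response rates, both between weeks 8 and 12 and 20 and 24") and tolerability: "The proportion of patients experiencing adverse effects and discontinuing treatment because of them will be reported". The form of presentation is the same throughout: "All these variables will be presented with their corresponding 95% confidence intervals". The section contains no difference, ratio, interaction or test.

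Association is treated separately, under Response predictors. There "the dependent variable will be the presence of a 50% response between weeks 8 and 12 of treatment", and in the univariate step "all study variables, demographic, clinical, and treatment-related will be evaluated". The significance level ("A statistical significance level of 0.05 will be considered") and the false discovery rate adjustment are also stated there.

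**The concern.** Three features make the subgroup plan look incomplete.

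- **No complement is named.** Women are listed without men, and older patients without younger ones.
- **Two groups overlap.** Every patient over 80 is also over 65, so those two rates are not independent and cannot be contrasted as if they were.
- **The regression covers one outcome.** Sex and age fairly count as demographic variables, but the model's dependent variable is only 50% response at weeks 8 to 12. Tolerability, which the plan singles out for these groups, has no model.

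A reader who wanted to know whether women tolerate treatment less well than men might compare the women's rate with the total. The total contains the same women, so the visible gap understates the real one, and overlap of the two intervals is not a test. A statement that women or older patients differ in tolerability, in the 30% or 75% rates, or at weeks 20 to 24 would have no planned estimate behind it.

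**Working it through.** The SAP gives no sample size, sex or age distribution, or event count. There is no figure of its own to reproduce, and every count below is an assumption.

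**1. How many outcomes lack a model.** Response: 3 thresholds × 2 windows = 6. Tolerability: adverse effects, and discontinuation because of them = 2. Total 6 + 2 = 8. The regression covers 1, leaving 7 (6 of 7 if the tolerability sentence is read as one proportion). This part of the concern is factually right.

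**2. Dilution when a group is compared with a whole that contains it.** With women *w*, men *m* and total *N*:

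p_w − p_total = (n_m / N) × (p_w − p_m)

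If women are 60–75% of patients (assumed), men are 40–25%, and the women-minus-total gap is 40–25% of the real difference. Example on assumed counts for discontinuation because of adverse effects:

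| Group | Count | Rate | Wilson 95% CI |
|---|---|---|---|
| Women | 40/200 | 20.0% | 15.0–26.1 |
| Total | 48/300 | 16.0% | 12.3–20.6 |
| Men | 8/100 | 8.0% | 4.1–15.0 |

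Women minus total is 20.0 − 16.0 = 4.0 points, which equals (100/300) × 12.0. Women minus men is 12.0 points, Newcombe 95% CI 3.4 to 19.2. At half the size (20/100 against 4/50) the same 12 points has a CI of −0.7 to 22.1.

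For age, again on assumed counts: over 80, 6/15 = 40.0%; over 65, 10/55 = 18.2%; over 65 to 80, 4/40 = 10.0%. The nested gap is 40.0 − 18.2 = 21.8 points, and the gap between disjoint bands is 30.0 points (Newcombe 95% CI 6.0 to 55.0).

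The algebra is correct. It shows that one comparison, subgroup against total or nested group against parent, would mislead as an estimate of a between-group difference. The SAP does not plan that comparison.

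**3. What the planned outputs estimate.** In the same example the women's 20.0% (15.0–26.1) is an unbiased estimate of the rate in women, whatever the men's rate is. Likewise 18.2% estimates the rate in all patients over 65, and 40.0% the rate in those over 80. The overlap of the age groups affects neither estimate. It would matter only if the two were contrasted.

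**4. Where the plan puts inference.** Setting the two sections side by side:

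- Secondary outcomes: rates within groups, with intervals. No hypothesis and no comparison.
- Response predictors: which variables go with a greater chance of response. Here the SAP states the model, the 0.05 level and the multiplicity adjustment.

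The two sections do different jobs and do not contradict each other.

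**5. Whether the complements are lost.** The SAP's opening paragraph plans to present variables as frequency and percentage. Its wording is clumsy, but the natural reading covers yes/no variables such as response and adverse effects. If counts are shown, the missing groups follow by subtraction: 48/300 less 40/200 gives 8/100 men, and 10/55 less 6/15 gives 4/40 aged over 65 to 80.

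**6. What adding contrasts would bring.** Women against men, and each of two older bands against those up to 65, make 3 contrasts. On 8 outcomes that is 3 × 8 = 24. If nothing differed, 24 × 0.05 = 1.2 would be expected to exclude zero.

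**The case for a change.** The strongest case for the concern is that singling out women and the elderly invites the question of whether they differ, and the planned tables do not answer it. On assumed counts, 24/60 women with adverse effects (40.0%, 95% CI 28.6–52.6) is compatible with a difference from men of +30 points if 4/40 men are affected and −35 points if 30/40 are. The SAP never labels these rates as descriptive only. Recovering complements by subtraction needs the counts to be printed, and gives a contrast that nobody prespecified.

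Part of this stands. If a later report asserted a sex or age difference in tolerability, or in a response rate other than the one modelled, the SAP would supply no planned estimate for it. That limits what may be concluded from the results.

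It does not make the plan wrong. The range from +30 to −35 points shows only that a rate in women does not determine a difference from men, and the SAP does not use it for that. A sentence labelling the rates descriptive would make explicit what the section already does. Requiring contrasts instead goes further, and reasonable statisticians would disagree on whether many unpowered comparisons improve the report.

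**Conclusion.** The concern does not hold. Its reading of the text is accurate: no complementary group, no between-group estimate, nested age groups, and a regression on one of eight proportions (or one of seven). But the SAP states a within-group aim, and rates with 95% confidence intervals meet it. Followed as written, no planned estimate is biased, and the primary outcome and the regression are untouched.

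The harm described depends on a comparison or claim that the SAP does not make. Its size cannot be derived from the document: the dilution to 25–40% assumes that women are 60–75% of patients, and the 12- and 30-point examples rest entirely on assumed counts. The conclusion rests on reading the subgroup sentence as descriptive. The absence of any test or difference in that section, and the placing of the significance level and multiplicity adjustment under Response predictors, support that reading.

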**Response predictors:**

To assess which variables are associated with a greater probability of response, a logistic regression analysis will be performed in which the dependent variable will be the presence of a 50% response between weeks 8 and 12 of treatment.

First, a univariate logistic regression analysis will be carried out in which all study variables, demographic, clinical, and treatment-related will be evaluated. Those variables with a *P* value lower or equal to 0.2 will be included in a multivariate model.

A statistical significance level of 0.05 will be considered. For the adjustment for multiple comparisons, the adjustment according to False Discovery Rate will be used using the Benjamini-Hochberg method.

Statistical analysis will be performed using SPSS (IBM).

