### **Response rate:**

#### *Primary outcome:*

The main study variable will be the 50% response rate evaluated between weeks 8 and 12 of treatment, compared to the baseline. The baseline period will be defined as the month prior to the treatment onset.

For its calculation, the percentage of patients who present a reduction in the number of headache days per month of at least 50%, compared to the month prior to the start of treatment, will be calculated.

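### The univariate P ≤ 0.2 screen exempts neither treatment nor baseline headache days, so the SAP's only adjusted model for treatment can lose treatment itself or its main severity covariate

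*SAP*

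**What the plan says.** The purpose of the regression is given in the SAP section *Response predictors*: "To assess which variables are associated with a greater probability of response, a logistic regression analysis will be performed". The outcome is the primary endpoint: "the dependent variable will be the presence of a 50% response between weeks 8 and 12 of treatment".

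The first step is univariate, and in it "all study variables, demographic, clinical, and treatment-related will be evaluated". The second step is fixed by one rule: "Those variables with a *P* value lower or equal to 0.2 will be included in a multivariate model". No variable is exempt from it. On significance the section adds "A statistical significance level of 0.05 will be considered" and, for multiplicity, "the adjustment according to False Discovery Rate will be used using the Benjamini-Hochberg method".

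Baseline headache days appear in the *Primary outcome* section only as the reference for the percentage reduction: "The baseline period will be defined as the month prior to the treatment onset". They are not named as a covariate, though they are presumably among the clinical candidates.

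Elsewhere the SAP gives response rates with 95% confidence intervals, and subgroups by sex and age. It gives no contrast between treatments, no list of confounders and no propensity method.

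**The concern.** The study title speaks of treatments in a real-world setting, and the SAP describes no random allocation. If clinicians tend to give the more effective treatment to patients with more headache days, and those patients respond less often, the benefit of treatment and the handicap of severity pull the unadjusted comparison in opposite directions. Either variable, or both, can then show an unadjusted P above 0.2 although each matters once the other is held fixed. An unadjusted P value cannot show whether a variable confounds.

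Two failures follow from applying the rule exactly:

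- Treatment is dropped, and the study reports no association with response.
- Treatment is kept while severity is dropped, and the odds ratio from the multivariate model is not adjusted for severity.

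The section's own aim is to find variables associated with response, and treatment is an explicit candidate. Missing a true association is therefore a failure even when the analysis is read purely as a predictor search.

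**Working it through.** **No figure to reproduce.** The SAP states no sample size, effect size, event count or power, so the inputs below are assumptions chosen to show a range.

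**Inputs.**
- From the SAP: entry at univariate P ≤ 0.2, significance level 0.05 (taken as two-sided).
- Assumed: two treatments, A and B; severity S standard normal; P(A) = expit(gS); logit P(response) = -b/2 + b·A + c·S, with b = ln 2.5 = 0.916; n = 200, about 100 per treatment. Here g is the selection log-odds ratio per SD and c the severity log-odds ratio per SD. The Benjamini-Hochberg step is left out.

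**Step 1: what the unadjusted comparison sees.** Let φ be the standard normal density. The response probability on A, averaged over the severity of those given A, is

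p_A = ∫ expit(b/2 + cS) · 2·expit(gS) · φ(S) dS,

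and by symmetry p_B = 1 - p_A.

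For g = 1.0 and c = -0.5, p_A = 0.560 and p_B = 0.440. Then:
- unadjusted log-OR = 2·ln(0.560/0.440) = 0.48, an OR of about 1.62 against the true 2.5
- SE = √(2 / (100 × 0.560 × 0.440)) = 0.285
- z = 0.48/0.285 = 1.68

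The P ≤ 0.2 screen needs |z| ≥ 1.28, so the chance that treatment is dropped is Φ(1.28 - 1.68) - Φ(-1.28 - 1.68) ≈ 0.34. Simulation gives 34% to 35%.

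**Step 2: the range.** The unadjusted OR and the chance of being dropped come from the formulas in step 1. Power for treatment is simulated, comparing the screen followed by a joint model with a joint model that always contains treatment and severity.

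| g | c | p_A / p_B | Unadjusted OR | Treatment dropped | Power, screen | Power, forced |
|---|---|---|---|---|---|---|
| 1.0 | -0.7 | 0.539 / 0.461 | 1.36 | 57% | 41% | 79% |
| 1.0 | -0.5 | 0.560 / 0.440 | 1.62 | 34% | 60% | 81% |
| 0.5 | -0.5 | 0.580 / 0.420 | 1.90 | 17% | 80% | 84% |
| 0 | -0.5 | 0.607 / 0.393 | 2.38 | 4% | 87% | 87% |
| 1.0 | +0.5 | 0.653 / 0.347 | 3.56 | 0.1% | 82% | 82% |

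With 2000 runs the Monte Carlo standard error near 80% is √(0.8 × 0.2/2000) ≈ 0.9 points. Repeat runs of the moderate-selection row gave 80% to 82% against 84% to 87%.

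**Step 3: sample size.** With g = 1.0 and c = -0.5 at n = 100, treatment is dropped in 53% of runs and power is 35% vs 51%. A larger study does not always cure the problem: with c = -0.7 at n = 300, treatment is still dropped in about half the runs.

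**Step 4: the unadjusted odds ratio.** With g = 1.0 and c = -0.5, treatment is kept while severity is dropped in 26% of runs at n = 100 and 19% at n = 200. At n = 200 the median OR in those runs is 2.0 against a true 2.5. It exceeds the 1.62 of step 1 because only runs that passed the screen are counted.

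**Step 5: false positives.** With no treatment effect, forced entry keeps the error rate near 5%, so the gain in power is not bought with false positives.

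**Step 6: a smaller true effect.** With a true OR of 2.0 and c = -0.5, power at n = 200 is 33% vs 56% for g = 1.0 and 54% vs 62% for g = 0.5. At n = 300 with g = 0.5 it is 71% vs 79%.

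**The case against.** The strongest reply is that the SAP states no treatment comparison. The section is a search for predictors, the primary outcome is a single responder percentage, and confounding by indication is a defect of a causal contrast. This stands as a limit on the point: a reader might infer that the plan contains a confounded treatment comparison, but it names none. The screen matters to the extent that a treatment association is read from this model.

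Second, the SAP does not say how treatment is chosen, how many treatments there are or how many patients take each. That severity guides choice is inferred from the real-world setting alone, and a treatment contrast or confounder list could sit in the protocol, which is not shown. This also stands, so the point is conditional.

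Third, a reader might argue that regression to the mean makes the screen worse, because response is a percentage change from one baseline month. That mechanism would make higher baseline days raise response. In that direction the screen does almost no harm (82% vs 82%), so regression to the mean does not support the claim of lost power.

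Fourth, the size depends on the scenario, and the large losses need strong selection. The simulations also omit the Benjamini-Hochberg step, whose family the SAP does not define, so the absolute power figures are not those of the plan.

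What the objections leave is that the rule is stated, admits no exception, and can lose a real association or its adjustment in a setting that the SAP does nothing to exclude.

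**Conclusion.** The point holds in a conditional form. The rule allows treatment, or the baseline measure against which response is defined, to be left out of the one model that could adjust one for the other. At n = 200 with a true OR of 2.5 and c = -0.5, the cost runs from nothing without selection, through about 4 points of power with moderate selection (84 - 80), to about 21 points with strong selection (81 - 60).

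This rests on assumed sample size, effects and selection, on severity lowering response, and on two treatments. None of these comes from the SAP. It is a cheap improvement to a secondary analysis. The documents do not support reading it as a threat to the primary responder percentage, which does not pass through this model.

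**What to change.** In the SAP section *Response predictors*, state that treatment and the number of headache days in the baseline month stay in the multivariate model whatever their univariate P value, and that the P ≤ 0.2 screen applies only to the remaining candidates. State how sparse treatment classes will be grouped. Take any treatment odds ratio that is interpreted from the adjusted model, and still report the planned univariate results, labelled as unadjusted.

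The change is one of wording. Baseline headache days are already needed for the primary outcome, so no new data are required. The price is a few degrees of freedom: one for baseline days, and one fewer than the number of treatment groups kept. With many small classes and few events that price rises, which is why the grouping rule should be fixed in advance.

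### The P ≤ 0.2 entry rule puts no limit on the size of the predictor model, so its odds ratios are likely to be exaggerated unless the smaller outcome group is large

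*SAP*

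**What the plan says.** The SAP's section on response predictors sets out the model-building procedure.

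- **Outcome:** "the dependent variable will be the presence of a 50% response between weeks 8 and 12 of treatment".
- **Candidates:** in the univariate step, "all study variables, demographic, clinical, and treatment-related will be evaluated".
- **Entry:** variables with a P value "lower or equal to 0.2 will be included in a multivariate model".
- **Inference:** "A statistical significance level of 0.05 will be considered", and for multiple comparisons "the adjustment according to False Discovery Rate will be used using the Benjamini-Hochberg method".
- **Software:** SPSS.

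The section gives no maximum number of predictors, no fixed list, no rule on how a construct is coded, no penalty or shrinkage, and no internal validation. That the model is an ordinary maximum-likelihood fit is an inference: the SAP says only that "a logistic regression analysis will be performed" and names no penalised method. The SAP does not state the sample size, the expected response rate or the number of candidate variables.

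**The concern.** Two mechanisms push the odds ratios away from 1. The first is selection. A variable enters because its association looks strong in these patients, and the effect is then estimated in the same patients, so the chance part of the association is carried into the estimate. The second is model size. Maximum-likelihood logistic estimates are biased away from 1 when the smaller outcome group is small relative to the number of parameters, and this rule does not bound that number.

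The multiplicity step does not help, because Benjamini-Hochberg changes which P values are declared significant and leaves the coefficients as they are.

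This is the only multivariable analysis in the SAP, and readers will take its odds ratios as the strength of each predictor. If those are inflated, they will not reproduce in new patients. Because the SAP states a rule, this is not detail left to the protocol: a sample size given there would change how much harm the rule does but would not add a limit or a correction to it.

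**Working it through.** **Inputs.** From the SAP: the binary outcome, all study variables as candidates, univariate P ≤ 0.2, then one logistic model. Everything else below is an assumption. The SAP states no figure that could be reproduced.

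**Step 1: variables entering by chance.** For K independent candidates with no association, the expected number entering is 0.2 × K, and the chance that at least one enters is 1 − 0.8^K.

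- K=10: 2 expected, probability 0.893
- K=20: 4 expected, 0.988
- K=30: 6 expected, 0.999
- K=40: 8 expected, above 0.999

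**Step 2: inflation of real predictors.** The procedure was simulated with 20 or 35 uncorrelated candidates, half continuous and half binary. Four were real (log odds ratio 0.4 per SD if continuous, 0.7 if binary), and about 50% responded. The measure is the median ratio of estimated to true log odds ratio among real predictors that passed the screen. The last column applies the factor to a true log odds ratio of 0.4, so exp(0.4) = 1.49; for example, exp(1.56 × 0.4) = 1.87.

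| n | SAP rule, factor | True OR of 1.49 reported as about |
|---|---|---|
| 80 | about 1.56 | 1.87 |
| 100 | 1.35-1.45 | 1.72-1.79 |
| 200 | 1.09-1.12 | 1.55-1.57 |
| 300 | 1.03-1.07 | 1.51-1.53 |

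A prespecified model holding the four real predictors gave 1.00-1.07 over the same range of n.

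**Step 3: a second set of assumptions.** Here there were 15 or 30 independent continuous candidates and 3 real predictors with a true OR of 1.5 per SD. The factor is ln(mean OR) / ln(1.5), with ln(1.5) = 0.405. Paired figures are K=15, then K=30. EPV is the median size of the smaller outcome group per variable entered.

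| N, response | EPV | Mean OR (truth 1.5) | Factor |
|---|---|---|---|
| 50, 50% | 5.8, 3.3 | 2.10, 2.40 | 1.83, 2.16 |
| 100, 50% | 10.0, 6.3 | 1.75, 1.77 | 1.37, 1.40 |
| 100, 30% | 7.5, 4.4 | 1.77, 1.82 | 1.41, 1.47 |
| 200, 50% | 18.8, 12.1 | 1.55, 1.58 | 1.08, 1.13 |
| 200, 30% | 12.6, 7.9 | 1.59, 1.61 | 1.14, 1.17 |
| 400, 50% | 36.9, 23.6 | 1.51, 1.52 | 1.02, 1.04 |

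The two sets agree closely at 100 and 200 patients. Variables with no effect that passed the screen had a mean absolute effect, expressed as an OR, of 1.9-2.3 at N=50, 1.5-1.6 at N=100, 1.3 at N=200 and 1.2 at N=400.

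**Step 4: the same data without the screen.** Predictors were drawn without looking at the outcome, and their number was capped at the smaller outcome group divided by 10 (an illustrative cap, not one from the SAP). Ordinary logistic regression then gave a mean OR for real predictors of 1.44-1.55 against the true 1.5 at every N. For variables with no effect, the mean absolute OR fell to 1.29-1.30 at N=50, 1.19-1.21 at N=100, 1.13-1.14 at N=200 and 1.09-1.10 at N=400. Most of the systematic inflation of real predictors therefore comes from the uncapped screen.

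**The case against.** The strongest objection is that the harm depends on numbers the SAP does not give and that may stand in the protocol. At N=400 the mean OR of real predictors is only about 1-2% too high (1.51-1.52 against 1.5), and at n=300 the log odds ratio is inflated by 3-7%. This stands. A reader might infer that the odds ratios are bound to be too extreme; without a sample size or candidate count, the document supports only a conditional statement.

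A reader might also infer that the rule doubles effects in a small study. Among real predictors that also reach P<0.05 at n=80, the factor under the SAP rule is indeed about 2.0-2.2. But a model prespecified with exactly the right four predictors gives about 1.7-1.8 under the same filter. Most of that excess comes from reading only significant results at low power, so it cannot be charged to the entry rule.

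Out-of-sample calibration slopes were well below 1 (0.18-0.69 in the four-predictor setting). They might suggest a larger fault, but the SAP plans an association analysis and no risk score. At N=400 the slope was still 0.66-0.79 while the odds ratios of real predictors were almost unbiased, so the slope does not measure how far each odds ratio is inflated.

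The over-65 and over-80 groups might be thought to enter the model beside age. The SAP names them as subgroups for describing response and tolerability and does not say that they are model terms.

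Finally, penalised regression is not shown to be necessary: step 4 reaches nearly unbiased odds ratios without it. What survives is that the rule has no limit, selects on the outcome, and is not corrected anywhere in the plan.

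**Conclusion.** The point holds in conditional form. The entry rule sets no limit on model size and nothing in the plan corrects the estimates, so the odds ratios are likely to be exaggerated unless the smaller of the responder and non-responder groups is large relative to the variables entered. Under the assumptions of step 2, the inflation on the log-odds scale is substantial at 80-100 patients, modest at 200 and slight at 300. The direction was the same in every setting tried; the size rests on assumed sample size, response rate, candidate count and effect sizes. Correlated candidates or sparse categories could behave differently.

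The effect is confined to the predictor analysis. The primary 50% response rate and the secondary rates with their confidence intervals do not depend on it. The change is worth making because it is cheap and this is the SAP's only multivariable result.

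**What to change.** In the section on response predictors, replace the P ≤ 0.2 entry rule with a list of baseline predictors fixed before analysis and without looking at the outcome, with one coding per construct. State a limit on the number of parameters, tied to the smaller of the responder and non-responder groups. As an illustration only, a divisor of 10 with 100 patients would allow 50/10 = 5 parameters at 50% response and 30/10 = 3 at 30%.

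If the screen is kept, bootstrap the whole procedure, repeating the screen in each resample, and report shrunken odds ratios beside the unshrunken ones. A penalised fit such as Firth or ridge is optional.

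The cost is SAP wording, with no new patients or data. The drawbacks are that fewer predictors, or smaller odds ratios, will be reported, and that the bootstrap option needs a short script beyond the standard SPSS menus.
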